In vitro assessment of hormone-responsive breast cancer: Immunohistochemical (IHC) assays of ER and PgR have numerous shortcomings; better predictive assays are needed. Selection of ET is based on hormone receptor status of the breast cancer, which is routinely assessed by in vitro IHC assays that have increasingly replaced quantitative radioligand binding assays. IHC determinations of hormone receptor status in breast carcinoma are equally sensitive, and more specific than biochemical determinations by ligand binding (Rhodes A. *J Clin Pathol* 2000;53:292-301; Hammond ME. *Arch Pathol Lab Med* 2010;134:e48-72.). However, while the results of IHC assays provide some predictive value in selecting the best follow up therapies, as noted above, even in ER+ disease, response rates to ETs are only approximately 50%. Furthermore, IHC assays of ER and PgR have a number of other shortcomings: (a) Most notably, they provide limited information about the functional status of the receptors and the responsiveness of tumor to ET, as described above. (b) The evaluation criteria to establish the positivity of ER and PgR are also not uniform in different laboratories, and widely ranging cutoff values for distinguishing positive from negative results have been used in IHC assays for both receptors. For example, a positive result can be considered the presence of greater than 1% or 5%, or even 10%, IHC-positive cells (Elledge RM. *Int J Cancer* 2000;89:111-117). (c) A recent systematic review of the literature on the use of IHC for evaluation of ER and PgR found that up to 20% of current IHC test results worldwide may be inaccurate (false negatives or false positives) (Hammond ME. *Arch Pathol Lab Med* 2010;134:e48-72). (d) Also, tumors are heterogeneous, and fine needle or core biopsies may miss important regions of the tumor. (e) Finally, in recurrent or metastatic breast cancer, the ER or PgR status of the lesions may not always be the same as that of the original primary tumor. Indeed, the receptor status of recurrent or metastatic disease may be more predictive of response to ET. However, because metastatic lesions often are not amenable to biopsy and because the biopsy of multiple lesions is impractical, the receptor status of individual lesion(s) cannot be easily determined.

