3.0 PATIENT SELECTION

3.1 Inclusion Criteria

1. Patient must be postmenopausal defined as meeting one or more of the following:
 - a. Age \geq 60 years
 - b. Amenorrheic for at least 12 months
 - c. Surgically sterile- having undergone bilateral oophorectomy,
 - d. FSH laboratory test level in postmenopausal range according to institutional standards (note FSH lab test must be ordered as standard of care to determine best treatment option and should not be ordered simply to confirm eligibility to this study)

- e. OR Pre-menopausal for whom standard ET is planned with ovarian suppression (imaging on study should be completed prior to start of ovarian suppression)
- 2. Patient must have histological or cytological confirmed breast cancer and fall into one of the following categories:
 - a. New diagnosis with plans for at least 6 months of neoadjuvant ET or any amount of neoadjuvant ET if surgery is planned as this will be used for response assessment .
 - b. Patients with newly diagnosed metastatic breast cancer or patient with known metastatic disease who has progressed while on therapy (no washout period is needed if the patient was treated with AIs or chemotherapy, but 2 months washout period is needed if the patient was treated with tamoxifen) who are going to be treated with ET.
- 3. Patient must have any one of the following types of breast cancer (primary or metastatic): ER+/PgR+/HER2– or ER+/PgR–/HER2–.
 - a. ER+ is defined as Allred score of at least 4 and greater.
 - b. PgR+ is defined as Allred score of at least 4 and greater.
 - c. IHC is the primary assay methodology for HER2. HER2– refers to HER2 of 0, 1+ by IHC or negative by fluorescence in situ hybridization (FISH)
- 4. Patient must have at least one measurable lesion according to RECIST 1.1 by radiological evaluation (ultrasound, mammography, MRI, CT, PET) or physical examination.
 - a. Patients with evaluable osseous metastasis that are lytic or mixed lytic-sclerotic are eligible.
 - b. Patients with hepatic lesions may be eligible provided the location of the lesion is peripheral or not too close to hepatic ducts. Decision on hepatic lesion eligibility will be made by the principal investigator or sub-investigator after careful review of all available imaging to ensure evaluation of the lesion will not be obscured by normal hepatobiliary excretion of ¹⁸F-FFNP.
- 5. Patient must be able to understand and willing to sign a written informed consent document.

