10.0 STATISTICAL CONSIDERATIONS

10.1 Study Objectives and Endpoints

The primary endpoints of the study are the change in ^{18}F -FFNP uptake following one-day of estradiol measured as the SUV, T/M and tumor-to-normal tissue ratio (T/N), and the response to ET among cancer patients (responders vs. non-responders). The secondary endpoint of the study is the immunohistochemical (IHC) determination of PgR status (PgR+ vs. PgR-) in ER+ breast carcinoma.

Study Design: This is a pilot study aiming to evaluate if response to ET of breast cancer can be predicated by the changes in tumor uptake of ^{18}F -FFNP after a one-day estradiol challenge test. The sampling method is non-random. The change of ^{18}F -FFNP uptake after estradiol will be correlated with responsiveness to ET. Additionally, an optimal threshold of the change in ^{18}F -FFNP uptake will be developed to differentiate therapy responding and non-responding patients. Also, the change in ^{18}F -FFNP uptake after estradiol challenge will be compared with the IHC determination of PgR status with respect to the prediction of ET responsiveness.

Accrual: The rate of accrual for the study is expected to be about 1 - 2 patients per month. It is expected that the accrual period of the study will be completed in 30 months with total 50 patients enrolled.

Power Analysis: It is estimated that the response rate to ET in the recruited patients will range from 20-50%. Using a 2-sided independent t-test with 80% power at a 0.05 significance level, a sample of 10 responders vs. 40 non-responders (i.e., 20% response rate) will allow us to detect a minimum of 101% SD between-group difference, where SD represents a pooled standard deviation of the ^{18}F -FFNP uptake changes among both therapy responding and non-responding patients; and a sample of 25 responders vs. 25 non-responders (i.e., 50% response rate) will allow us to detect a minimum of 80.9% SD between-group difference.

Data Analysis: Demographic and clinical characteristics of all the enrolled patients will be summarized using descriptive statistics. The changes in ^{18}F -FFNP uptake after estradiol challenge will be compared between responders and non-responders via

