Wilcoxon rank sum test. A receiver operating characteristic (ROC) curve will be plotted to identify an optimal threshold of ^{18}F -FFNP uptake change to determine a criterion for the future prediction of therapy responsiveness. The positive and negative predictive values (PPV and NPV) will be calculated for response to ET using both the ^{18}F -FFNP uptake-based criterion and IHC determination of PgR receptor status. Multivariate logistic analyses of therapy response will be used to examine prediction power among the changes in ^{18}F -FFNP uptake and PgR receptor status

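### In the logistic comparison, FFNP change is quantitative but PgR is only +/- at Allred 4; if PgR carries graded information, this coding favours FFNP even when the two markers are equally informative

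*Combined protocol and SAP*

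**What the plan says.** Objective 2.1.2 (Section 2.0) asks whether FFNP change identifies responders to endocrine therapy better than PgR by IHC. Section 10.1 makes the comparison in two ways:

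- **PPV and NPV**, using an FFNP cutoff taken from the study's ROC curve on one side and PgR status on the other. Both markers are binary here.
- **A logistic model:** "Multivariate logistic analyses of therapy response will be used to examine prediction power among the changes in" FFNP uptake and PgR receptor status.

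The secondary endpoint is the IHC "determination of PgR status (PgR+ vs. PgR-) in ER+ breast carcinoma". Section 3.1 fixes the cut: "PgR+ is defined as Allred score of at least 4 and greater". Section 6.5 measures FFNP change as absolute and percent change in uptake, which is a quantitative scale. Section 10.1 does not use the word continuous. But it names the cutoff-based FFNP criterion separately, for PPV and NPV, so the plain reading is that the logistic model takes FFNP change uncut. The Allred score appears nowhere in Section 10.

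**The concern.** Cutting a graded marker at one point loses information. If only one of two competing markers is cut, the other tends to win for that reason alone. A larger contribution from FFNP in the logistic model could then be reported as FFNP being the more informative marker when it partly reflects how PgR was coded.

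The protocol's rationale treats PgR as graded. Section 1.1 considers what low PgR levels may mean in ER+ disease, and Section 1.3 objects to the view that PgR levels lack predictive value. Section 1.1 also criticises IHC because "widely ranging cutoff values for distinguishing positive from negative results have been used in IHC assays for both receptors". A comparison resting on a single cut sits awkwardly with that argument.

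**Working it through.** **1. The plan's own figures.** The power statement in Section 10.1 assumes a two-sided t-test at the 5% level with 80% power, and 50 patients in all. For the lowest response rate considered it reads: "a sample of 10 responders vs. 40 non-responders (i.e., 20% response rate) will allow us to detect a minimum of 101% SD between-group difference". For an even split of 25 and 25, the plan says that the sample "will allow us to detect a minimum of 80.9% SD between-group difference". Solving the noncentral t distribution (48 df) for 80% power gives 1.011 SD (10 v 40) and 0.809 SD (25 v 25). Both figures reproduce. They serve below as the common effect size d for the two markers.

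**2. Information lost by one cut (closed form).** For normal markers with a responder/non-responder difference of d SD:

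- Uncut: AUC = Φ(d/√2). For d = 0.809 this is Φ(0.572) = 0.716; for d = 1.01 it is Φ(0.714) = 0.762.
- Cut once: AUC = (sensitivity + specificity)/2, at most Φ(d/2). For d = 0.809 the ceiling is Φ(0.4045) = 0.657; for d = 1.01 it is Φ(0.505) = 0.693.
- Away from the best cut the loss is larger. With 85% PgR+ and 25 v 25, (0.937 + 0.237)/2 = 0.587.

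**3. The planned logistic comparison (simulation).** Write l_F, l_P and l_FP for the maximised log-likelihoods with FFNP alone, PgR alone and both. In the joint model the likelihood-ratio statistic for FFNP is 2(l_FP − l_P) and for PgR 2(l_FP − l_F). FFNP's is the larger exactly when l_F > l_P.

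Assumptions not in the documents: normal latent markers; PgR+ prevalence of 50%, 70% or 85%; marker correlation r of 0 or 0.5; an eight-level Allred score (0, 2-8) with levels equally frequent on each side of the cut. There were 1,000 trials of 50 patients per row, with a simulation error of about √(0.5 × 0.5/1000) = 1.6 percentage points.

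Share of trials in which FFNP has the larger statistic, both markers equally informative:

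| Responders v non-responders, d | r | PgR+ | PgR as +/- | PgR as Allred score |
|---|---|---|---|---|
| 25 v 25, 0.809 | 0 | 50% | 65% | 52% |
| | 0 | 70% | 68% | 51% |
| | 0 | 85% | 78% | 56% |
| | 0.5 | 50% | 67% | 51% |
| | 0.5 | 70% | 73% | 56% |
| | 0.5 | 85% | 79% | 52% |
| 10 v 40, 1.01 | 0 | 50% | 67% | 54% |
| | 0 | 70% | 74% | 57% |
| | 0 | 85% | 87% | 53% |
| | 0.5 | 50% | 73% | 55% |
| | 0.5 | 70% | 77% | 55% |
| | 0.5 | 85% | 90% | 56% |

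A separate run over the same ranges gave 63-90% and 50-58%; these wider limits are the ones quoted in the conclusion.

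**4. Significance in the joint model at 70% PgR+ (FFNP v PgR).**

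| Case | PgR as +/- | PgR as Allred score |
|---|---|---|
| 25 v 25, r = 0 | 78% v 51% | 75% v 73% |
| 25 v 25, r = 0.5 | 58% v 21% | 37% v 32% |
| 10 v 40, r = 0 | 79% v 47% | 75% v 69% |
| 10 v 40, r = 0.5 | 64% v 20% | 37% v 31% |

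**5. Where the effect disappears.**

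- No signal in either marker (d = 0): FFNP has the larger statistic in 48-51% of trials against PgR+/-.
- PgR information only in +/- status, FFNP given the same AUC (0.625-0.70), independent markers, 10-25 responders, 1,500 trials each: FFNP has the higher AUC in 48-53%. A linear Allred score then lowers the power to see that PgR adds to FFNP from 45-88% to 25-70%.

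**The case against.** The strongest reply is that PgR+ versus PgR- is the declared endpoint, cut at one fixed point in Section 3.1. Comparing a new test with the standard marker as categorised is a legitimate question. That stands, and it is why the declared comparison should stay. It limits what a win for FFNP means; it does not make the coding neutral.

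The effect also depends on PgR having a graded signal. Section 1.1 reports that up to 20% of IHC results may be inaccurate, and Section 1.3 notes that PgR assays are not controlled for endogenous estradiol. Both weaken the assumption that the Allred score captures such a signal. This stands too: the advantage is conditional, and replacing PgR+/- by a linear score could handicap PgR instead.

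A reader might infer more than the documents support:

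- *That the whole FFNP-versus-PgR comparison is affected.* PPV and NPV, which are closest to the sensitivity and selectivity wording of objective 2.1.2, use two binary markers. Choosing the FFNP cutoff on the same patients is a different issue.
- *That the size should be read from AUCs.* Under the assumptions of the working, FFNP has the higher AUC in 73-99% of trials against PgR+/-. But Section 10.1 plans an ROC curve only to find the FFNP threshold, with no AUC comparison. The likelihood-ratio figures are the relevant ones.
- *That the Allred score is discarded at data level.* The case report form fields are not shown, and Sections 4.1 and 7.0 collect eligibility source documents. Only the score's absence from the analysis plan is established.
- *That the protocol calls IHC cutoffs arbitrary.* It says that they are not uniform between laboratories.

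Finally, this is a pilot study with no superiority test or decision rule for FFNP over PgR. That lowers the stakes, but the comparison is a stated objective and its result will be interpreted.

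**Conclusion.** The point holds for the logistic analysis only, and only if PgR carries graded information. Then, with equally informative markers (0.81-1.01 SD each), 15-50% PgR-negative and correlation 0 to 0.5, FFNP has the larger likelihood-ratio statistic in about 63-90% of 50-patient trials when PgR is +/-, against 50-58% when the Allred score is used. The size rests on the assumed prevalence and correlation, neither of which the documents give; the direction is the same throughout those ranges. Quantitative entry of FFNP change is the plain reading of Section 10.1, not an explicit statement. As planned, a stronger FFNP term would support a conclusion about FFNP versus dichotomised PgR status, but would not show that FFNP is the more informative marker.

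**What to change.** In Section 10.1, state that FFNP change enters the logistic model undichotomised, and keep the PgR+/- comparison as declared. Add one pre-specified companion analysis: enter the Allred score as an ordinal term in the same model, and report its AUC beside that of FFNP change, with a paired (DeLong) 95% CI for the difference. State in advance that FFNP will be described as the more informative marker only if its advantage persists against the graded score; otherwise the conclusion is limited to FFNP versus PgR status as dichotomised.

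The cost is one more analysis, a few sentences and, if the score is not already recorded, one case report form field, since classification at Allred 4 already needs the score. FFNP may look less superior. A linear score can lose power if the PgR signal lies only at the cut, which is why the PgR+/- analysis is retained.

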2.0 OBJECTIVES

Our hypothesis is that change in ¹⁸F-FFNP uptake following 1-day of estradiol is a strong predictor of response to ET in patients with hormone-sensitive (ER⁺/± PgR⁺)/HER2- breast cancer. We believe the increase in tumor PgR after 1-day estradiol will be more reliable than a decrease after estrogen deprivation, particularly because most breast cancer patients are postmenopausal and basal PgR levels will be low due to the low endogenous, menopausal estrogen levels. Thus, we propose to use a hormone-challenge test for assessment of functional

ER based on the change in ^{18}F -FFNP uptake before and after a 1-day estradiol challenge in patients with ER+ metastatic breast cancer. We expect that the changes in ^{18}F -FFNP uptake to be a highly reliable means to predict a favorable response of ER+ breast cancer to ET. We propose to study patients with biopsy-proven new diagnosis of ER+ metastatic/recurrent breast cancer who are going to be treated with ET (tamoxifen, AI agents or faslodex) according to standard of care.

2.1. Evaluate whether the change in tumor uptake of ^{18}F -FFNP following a 1-day estradiol challenge differs among patients who respond to ET versus those who do not respond.

2.1.1 Determine the optimum cutoff value for change in tumor ^{18}F -FFNP uptake after estradiol to distinguish responders from nonresponders.

2.1.2 Evaluate whether the change in tumor uptake of FFNP can identify patients with hormone-sensitive disease who will respond to ET with greater sensitivity and selectivity than tumor PgR measured by IHC.

2.2 Evaluate the heterogeneity of tumor ^{18}F -FFNP uptake at baseline and after estradiol challenge in patients with multiple metastatic foci.

2.2.1. Explore whether response is related to ^{18}F -FFNP uptake heterogeneity. To assess the heterogeneity at the baseline, a comparison with FDG-PET/CT will be performed to map the metabolically active disease. Once the metabolically active disease is determined, FDG+/FFNP- will be considered as discordant lesions. At follow-up, the baseline FFNP-PET/CT will be correlated with follow-up FFNP-PET/CT to assess heterogeneity in response to estradiol.

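### Objective 2.1.2 asks whether FFNP change predicts response better than IHC PgR, but section 10.1 plans no estimate of the difference; its logistic model addresses added value instead

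*Combined protocol and SAP*

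**What the plan says.** The question is comparative in both places where it appears. Section 2.0, objective 2.1.2, asks whether the change in FFNP uptake can identify patients "who will respond to ET with greater sensitivity and selectivity than tumor PgR measured by IHC". Section 10.1 (Study Design) says that the change "will be compared with the IHC determination of PgR status with respect to the prediction of ET responsiveness".

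Section 10.1 (Data Analysis) has three steps that bear on it:

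- "A receiver operating characteristic (ROC) curve will be plotted to identify an optimal threshold of" FFNP uptake change. This covers FFNP only and serves to choose a cutoff.
- "The positive and negative predictive values (PPV and NPV) will be calculated for response to ET using both the" FFNP-based criterion and IHC PgR status. No difference, interval or test is mentioned.
- "Multivariate logistic analyses of therapy response will be used to examine prediction power among the changes in" FFNP uptake and PgR status. The model is not written out, and there is no rule for reading it.

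PgR enters as a two-level variable: the secondary endpoint is the "immunohistochemical (IHC) determination of PgR status (PgR+ vs. PgR" negative classification. Section 3.1 sets the positive class at an Allred score of at least 4. The sample is planned "with total 50 patients enrolled".

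**The concern.** To say that one marker predicts better than another, one needs an estimate of the difference between them in the same patients. None is planned. PPV and NPV will sit side by side without a difference or an interval, and they are not the sensitivity and selectivity that the objective names (I read selectivity as specificity).

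The only step that puts both markers into one inferential analysis is the logistic model. In a joint model, the FFNP coefficient is zero when FFNP carries no information beyond PgR. That is a different null from FFNP being no better than PgR. Two equally accurate markers that are not redundant both add information, so the FFNP term can be significant without FFNP being better. If the study reports only what section 10.1 lists, objective 2.1.2 has no direct answer, and the logistic p-value is the nearest thing to one.

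**Working it through.** **1. The two nulls.** Suppose both markers are normal within response group with unit SD, separations d_F (FFNP) and d_P (PgR), and within-group correlation ρ. The joint logistic coefficient for FFNP is then

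β_F = (d_F − ρ·d_P) / (1 − ρ²).

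It is zero when d_F = ρ·d_P, whereas the objective's null boundary is d_F = d_P. With equal markers, β_F = d/(1 + ρ). At d = 0.809 and ρ = 0.3 this is 0.809/1.3 = 0.62. With FFNP worse (0.92 v 1.19, ρ = 0.3) it is (0.92 − 0.357)/0.91 = 0.62, still clearly positive. The formula is exact for two normal markers; the simulations below use the planned scales.

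**2. The plan's own figures.** Section 10.1 gives detectable differences of 1.01 SD (10 v 40) and 0.809 SD (25 v 25) for a two-sided t-test at 0.05 with 80% power. Exact noncentral-t calculation returns 1.011 and 0.809, so both reproduce. Under normality with equal SDs, AUC = Φ(d/√2), giving 0.762 and 0.716.

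**3. How often the FFNP term is significant when the AUCs are equal.** FFNP change is continuous. PgR is binary, with sensitivity = specificity = the FFNP AUC, so both AUCs match. Entries are Wald, with likelihood ratio in brackets, at p < 0.05, from 2,000–4,000 trials per setting.

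| Within-group correlation | 10 v 40, AUC 0.762 | 25 v 25, AUC 0.716 |
|---|---|---|
| 0 | 61–64% (71–74%) | 67% (71–72%) |
| 0.3 | 38–40% (48–50%) | 41–44% (46–50%) |
| 0.6 | 21% (28–29%) | 23% (28%) |
| 0.9 | 7% (11%) | 7% (10%) |

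A second set-up takes its accuracy from the FES counts in section 1.3: 12 of 24 FES-positive and 5 of 27 FES-negative patients responded. Sensitivity is 12/17 and specificity 22/34, so the binary AUC is (0.706 + 0.647)/2 = 0.676. With FFNP at the same AUC and correlation 0 to 0.5, the likelihood-ratio rate is about 44% down to 18% (10 v 40) and 59% down to 26% (25 v 25). It is below 10% at 0.9. Together the two set-ups support roughly 20–60% over that range.

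**4. FFNP less accurate (AUC 0.70 v 0.78).** The FFNP term is still significant (Wald) in 34–52% of trials at correlation 0 and 17–24% at 0.3, but only 4–6% at 0.6.

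**5. A direct paired comparison under equality.** In the settings of step 3, a paired AUC test rejects in 5.0–7.3% of trials (two-sided). With a binary FFNP criterion at a fixed cutoff, McNemar's test of accuracy rejects in 2.0–3.7%.

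**6. The scale matters.** Take two equally informative underlying markers, each separated by 0.919 SD (the sum of the normal quantiles of 12/17 and 22/34). Left continuous, FFNP has AUC Φ(0.919/√2) = 0.742. PgR cut to two levels has 0.676. A paired AUC test then favours FFNP in about 11–16% of trials at correlation 0 to 0.5, only because PgR was dichotomised.

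**The case against.** A reader might infer that the plan will declare FFNP superior whenever its logistic term is significant, or that it has chosen the wrong test for a superiority claim. The documents do not support that. They attach no hypothesis, significance level or decision rule to the logistic step. The plural wording could also cover separate and combined models, so the joint model is an inference, though the natural one. This objection stands, and it limits the point to a missing estimate and an unlabelled model.

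It is also fair that a descriptive comparison is planned, since PPV and NPV are calculated for both markers. The counts behind them would yield sensitivity and specificity for each marker. They would not yield an interval for the paired difference, which needs the cross-classification of the two markers within responders and within non-responders.

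The simulated rates depend on a correlation that the documents do not give. FFNP images PgR itself, so high redundancy is possible, and the rate then falls to about 7–11%. On the other side, section 1.3 argues that static PgR assays are not controlled for endogenous estradiol, which is why the change after challenge is expected to carry different information. Neither argument settles the value, so the rates remain illustrations.

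Finally, section 10.1 calls the study a pilot and powers only the responder contrast. That argues against requiring a formal superiority rule. It does not argue against estimating the quantity that the objective names.

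**Conclusion.** The concern holds as a gap between objective and analysis. Objective 2.1.2 asks for a comparison of accuracy, and section 10.1 contains no estimate of the FFNP-minus-PgR difference. The one model that includes both markers, read as a joint model, answers whether FFNP adds to PgR.

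A significant FFNP term is therefore weak evidence that FFNP is better: with equal AUCs it appears in roughly 20–60% of trials at correlation 0 to 0.5 and about 10% or less at 0.9. These figures assume normal FFNP change, binary PgR and accuracies borrowed from the plan's detectable effects or its FES counts, and weaker markers give lower rates. That the markers carry different prediction questions does not depend on those assumptions; only the size does. The point deserves correction before analysis, but it does not affect the primary comparison of FFNP change between responders and non-responders.

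**What to change.** In section 10.1, for objective 2.1.2:

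- Report the paired FFNP-minus-PgR differences in sensitivity and in specificity, in the same patients, with 95% CIs. Use a patient-level bootstrap that repeats the cutoff selection in every resample and corrects for its optimism, because the FFNP cutoff is chosen in the same data while the PgR cutoff is fixed. State the rule that defines the optimal cutoff, so that it can be repeated.
- If an AUC difference is also reported, put both markers on the same scale: the binary FFNP criterion against PgR status, or continuous FFNP change against Allred score where recorded. Continuous FFNP against binary PgR favours FFNP.
- Keep the logistic model, write it out, and label it as assessing the added value of FFNP given PgR, not as evidence that FFNP is better.

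No formal superiority rule is needed. The cost is a few sentences and one analysis of data already collected.

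The drawback is precision. With independent markers of equal sensitivity p among n responders, the 95% half-width for the difference is about 1.96·√(2p(1 − p)/n). For p = 0.716 and n = 25 this is 1.96·√(0.407/25) = 0.25; for p = 0.762 and n = 10 it is 1.96·√(0.363/10) = 0.37. Both are before any allowance for cutoff selection; positive correlation between the markers would narrow them.
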